7.1.4 Physical examination

A baseline physical exam will be completed assessing the Cardiovascular, Respiratory and GI systems and this data recorded on the CRF. Any AEs/SAEs identified during the exam will be recorded/reported. Additional full physical examinations will be completed if AE/SAEs are reported, requiring a more thorough exam to be carried out. This will include assessment of local toxicity at the site of intravenous administration.

All new findings or changes to previous findings from vital signs or baseline physical exam considered clinically significant are to be recorded in the CRF, as an adverse event if the finding is made subsequent to the patient signing the ICF for the main study (See Section 11). If the patient has received a dose of study medication it should be deemed whether the AE is related or non-related to the study drug.

7.1.5 Pregnancy test

All women of childbearing potential must be screened for pregnancy by urine or serum hCG test as part of the eligibility assessment.

7.1.6 ECG

An ECG will be performed on resting patients at baseline, 2.5hr, 10hr and 20hr and any clinically significant deviations recorded.

7.1.7 Treatment Phase

Treatment will start with the first NAC bag of 100 mg/kg in 200 ml ("loading dose") at time point '0'. Immediately prior to PP100-01 a study specific blood sample will be collected (time 2hr).

PP100-01 treatment is administered intravenously as a bolus infusion over 5 minutes at the dose specified by the dosing cohort:

- Group A: PP100-01 (2 µmol/kg calmangafodipir) after the "loading" dose of NAC
- Group B: PP100-01 (5 µmol/kg calmangafodipir) after the "loading" dose of NAC
- Group C: PP100-01 (10 µmol/kg calmangafodipir) after the "loading" dose of NAC

All necessary precautions will be taken during administration of the study drug. The patient will be monitored with vital signs (Section 7.1.3). Observation and medical treatment for anaphylactic shock will, as a standard be requisite.

The 12hr NAC regime will be continued with the second dose: 200 mg/kg NAC in 1000 ml i.v. over 10 hr. As per routine clinical practice, there will be one blood sample taken 2 hrs before the end of the second NAC bag (the 10hr time-point) and a second blood sample taken 10h later (the 20hr time-point).

The following procedures should be performed during the treatment phase at time-points: baseline, 2hr, 10hr and 20hr (see study schedule, section 7.2 (Table 1)):

• ALT, bilirubin and alkaline phosphatase (ALP)

- Prothrombin time and INR
- Serum creatinine
- Biomarkers: CK18 and microRNA MiR122, GLDH, mitochondrial DNA and others
- PP100-01 level will be assessed at 2hr, 10hr and 20hr

Any rescue medication given will be recorded in the Case Report Form by routine clinical staff.

7.1.8 End of treatment

At the end of the 12hr NAC regimen the decision to continue NAC is made by assessment of the blood sample taken at the 10hr time-point:

- the ALT has more than doubled since the admission measurement, OR
- the ALT is two times the upper limit of normal or more, OR
- the INR is greater than 1.3 (in the absence of another cause, e.g. warfarin)
- paracetamol/acetaminophen concentration > 20 mg/mL

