Entry into the study will depend on the patient's blood results confirming the need for NAC. A total of 24 patients will be assigned into one of 3 dosing cohorts of 8 patients (N=6 for PP100-01 and NAC; N=2 for NAC alone).

The study will primarily evaluate safety and tolerability for treatment with PP100-01 in combination with NAC as compared to NAC alone.

Baseline Assessments:

Blood tests, vital signs, physical examination and an ECG will be completed as part of the baseline assessments.

NAC will be given to all patients arriving to the hospital according to the standard guidelines when paracetamol/acetaminophen overdose is suspected. All patients that arrive to the hospital within 24 hr of POD and require NAC treatment will be asked if they will participate in the study once their blood results are available. The following investigations will be performed as part of clinical care on arrival to hospital or 4hrs after overdose (whichever is the longer time):

- Paracetamol level in serum/plasma
- Urea and electrolytes and creatinine
- Liver function tests (LFTs) ALT, Bilirubin and ALP
- Clotting screen: INR and Prothrombin time (PT)

Treatment Phase:

Patients that have signed the informed consent will be treated with NAC and randomised to NAC alone (N=2 per dosing cohort) or PP100-01 and NAC (N=6 per dosing cohort)

- Group A: PP100-01 (2 µmol/kg calmangafodipir) after the "loading" dose of NAC
- Group B: PP100-01 (5 µmol/kg calmangafodipir) after the "loading" dose of NAC
- Group C: PP100-01 (10 µmol/kg calmangafodipir) after the "loading" dose of NAC

PP100-01 treatment is administered intravenously over 5 minutes.

The NAC regime will be continued with the second dose: 200 mg/kg NAC in 1000 ml i.v. over 10hr.

The following procedures should be performed during the treatment phase:

- ALT bilirubin and alkaline phosphatase (ALP)
- Prothrombin time and INR
- Serum creatinine
- Biomarkers: CK18 and microRNA MiR122, GLDH, mitochondrial DNA and others

End of treatment:

At the end of the 12hr NAC regimen the decision to continue NAC is made by:

- the ALT has more than doubled since the admission measurement, OR
- the ALT is two times the upper limit of normal or more, OR
- the INR is greater than 1.3 (in the absence of another cause, e.g. warfarin)
- paracetamol/acetaminophen concentration greater than 20 mg/mL

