3.1 Routine Medical Management of POD

[figure not shown]
A nomogram (Figure 1) is used to identify patients who require NAC treatment following a POD based on their APAP concentration, time from ingestion and presence or absence of factors which increase risk of hepatotoxicity such as enzyme inducers or conditions predisposing to low hepatic glutathione stores. Patients with timed plasma concentrations above the appropriate treatment receive treatment with the full 20.25hrs course of intravenous NAC. In patients presenting up to 8hrs after ingestion, the need for NAC treatment can be assessed once the plasma APAP concentration is known. In patients presenting later than 8h as well as staggered POD, NAC treatment is initiated if the patient has ingested greater than 12 g (or 150 mg/kg) paracetamol or,

[figure not shown]
if they have risk factors, greater than 7.5 g. The need for continuation of NAC is then based on the plasma APAP concentration.

At the end of 20.25hr NAC regimen the decision to continue NAC is made by:

- the ALT has more than doubled since the admission measurement, OR
- the ALT is two times the upper limit of normal or more, OR
- the INR is greater than 1.3 (in the absence of another cause, e.g. warfarin)
- paracetamol/acetaminophen concentration greater than 20 mg/mL

Those that meet these criteria will continue to receive further NAC infusions at the concentration of the 16-hourly infusion until these blood results improve.

Recent studies in the Edinburgh and Newcastle-upon-Tyne toxicology units show that following the 20.25h NAC treatment where the loading dose is infused during 15 min, 51 of 346 (14.7%) patients had evidence of hepatocellular injury as measured by a 50% increase in their ALT after admission. Of these 51 patients, only 8 subsequently developed overt evidence of hepatocellular dysfunction as measured by an INR>2.0. All patients who subsequently developed an INR>2.0 had at least a 50% increase in their admission ALT after NAC treatment.

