- To determine the occurrence of hepatotoxicity as determined at the end of the 12hr NAC administration regimen.
- To measure length of hospital stay in patients receiving co-treatment and 12hr NAC treatment regimens.
- Proportion of patients with a 50% increase in ALT after 10h post-treatment with NAC, compared with the admission value
- Proportion of patients with ALT>100 at 10h post-treatment with NAC
- Proportion of patients with INR>1.3 at 10h post-treatment with NAC
- Proportion of patients with paracetamol/acetaminophen concentration > 20 mg/mL

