6.2 Inclusion Criteria

- 1. Any patient with capacity admitted to hospital within 24 hrs either a single acute POD or more than one dose of paracetamol (staggered) and deemed to require treatment with NAC.
- 2. Provision of written informed consent
- 3. Males and females of at least 16 years of age

These patients will include:

a) Patients presenting within 8h of overdose who have a timed blood paracetamol concentration above the 100-line on the UK APAP overdose treatment nomogram (See Figure 1).

b) Patients presenting later than 8h who are at risk of liver injury from the reported dose ingested and have blood results confirming need for NAC

c) Patients presenting after taking a staggered APAP overdose (defined as when the overdose of APAP is taken over a period of more than 1hr)

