4.2 Baseline characteristics (FA)

The baseline patient characteristics listed in this section (recorded at either Screening, Timepoint 0 or Baseline [Pre PP100-01]) will be summarised by randomised treatment and overall for the FA population.

- Participant details
 - Age (years)
 - Height (cm)
 - Weight (kg)
 - Body Mass Index (kg/m²)
 - Ethnicity
 - Gender (male/female)

- Childbearing potential (yes/no) [Female participants only]
- Overdose details
 - Time from paracetamol ingestion to presentation at hospital (hrs)
 - Type of overdose (acute within 8hrs of NAC starting / acute more than 8hrs before NAC starting / staggered intentional / supratherapeutic / not known)
 - Amount of paracetamol ingested known (yes/no)
 - Total paracetamol ingested (g)
 - Other drugs ingested
 - Anticoagulants
 - Non-opioid analgesics
 - NSAIDs
 - Cardiovascular drugs
 - Alcohol
 - Opioids
 - SSRIs
 - Tricyclic antidepressants
 - Benzodiazepines
 - Other
- Concomitant medications during preceding 30 days (tabulated by category and whether ongoing)
- Physical examination (each classified as Normal / Abnormal not Clinically Significant / Abnormal Clinically Significant)
 - Cardiovascular
 - Respiratory
 - Gastrointestinal
- Vital signs
 - Systolic blood pressure (mmHg)
 - Diastolic blood pressure (mmHg)
 - Pulse (bpm)
 - Respiratory rate (per minute)
 - Temperature (°C)
 - Oxygen saturation (%)
- ECG (Normal / Abnormal not Clinically Significant / Abnormal Clinically Significant)
- Clinical bloods
 - Paracetamol level (mg/L)
 - INR
 - PT (sec)
 - ALT (U/L)
 - Alkaline phosphatase (U/L)
 - Bilirubin (µmol/L)
 - Creatinine (µmol/L)
 - Haemoglobin (g/L)
 - Urea (mmol/L)
 - MCV (fL)

- WBC ($\times 10^9/L$)
- Sodium (mmol/L)
- Potassium (mmol/L)

No formal statistical testing of baseline characteristics will be performed.

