4.5 Efficacy Secondary Outcomes (FA,PP)

Hepatotoxicity will be assessed using ALT and INR.

Descriptive summaries will be provided by treatment group and overall at each measurement time point during the treatment period (10 hours, 20 hours). Change from baseline to each of the 10 and 20 hour time points will be summarised by treatment group and overall for ALT and INR.

A graphical summary of each marker will be presented in a separate panel for each treatment group. Each will show the profile of the measurements for individual patients overlaid by the treatment group mean profile.

At each measurement time point during the treatment period (10 hours, 20 hours) ALT and INR will be analysed by treatment group and overall using the mean and 95% confidence interval. They will be compared within each dosing cohort between the PP100-01+NAC and the NAC alone patients using

¹ Note that PP100-01 is administered as a bolus and therefore cannot be stopped once the bolus has been given

the difference in means and its 95% confidence interval. The markers will be compared between each of the PP100-01 2µmol/kg, 5µmol/kg and 10µmol/kg groups and the combined NAC alone group in the same way. These analyses will be repeated using the change from baseline in ALT and INR, for absolute and relative change as appropriate.

Use of the natural log transformation of the data and the geometric mean summary statistic will be considered as appropriate in the descriptive, graphical and formal analyses of these markers.

Paracetamol level (mg/L) will be summarised descriptively and graphically by treatment group and overall at its baseline and 10 and 20hrs measurement time points in the same way as for the ALT and INR markers.

The following efficacy indicators will be summarised by treatment group and overall in the same manner as for the primary outcome analysis in Section 4.4.

- Proportion of patients with paracetamol/acetaminophen concentration >20 mg/L at 10 hrs
- Proportion of patients with paracetamol/acetaminophen concentration >20 mg/L at 20 hrs
- Proportion of patients with a 50% increase in ALT after 10 hrs, compared with baseline value
- Proportion of patients with a 50% increase in ALT after 20 hrs, compared with baseline value
- Proportion of patients who have doubled their ALT after 10 hrs, compared with baseline value
- Proportion of patients who have doubled their ALT after 20 hrs, compared with baseline value
- Proportion of patients with ALT>100 U/L at 10hrs

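### The protocol gives the paracetamol threshold for continuing NAC as 20 mg/mL, 1,000 times the SAP's 20 mg/L, so that criterion cannot be met as written

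*Protocol*

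**What the plan says.** The trial's rule for continuing NAC after 12 hours appears twice in the protocol. Section 7.1.8 applies it to the 10-hour sample and lists four criteria: two on ALT, one on INR, and "paracetamol/acetaminophen concentration > 20 mg/mL". The synopsis, under end of treatment, has the same list with "paracetamol/acetaminophen concentration greater than 20 mg/mL". Section 3.1, describing routine care with the 20.25-hour regimen, repeats that wording.

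Protocol section 4 carries the unit into an exploratory outcome, "Proportion of patients with paracetamol/acetaminophen concentration > 20 mg/mL", with no time point.

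The SAP does not restate the continuation rule. It lists baseline paracetamol in mg/L (4.2) and defines the matching outcomes in 4.5 as "Proportion of patients with paracetamol/acetaminophen concentration >20 mg/L at 10 hrs" and "Proportion of patients with paracetamol/acetaminophen concentration >20 mg/L at 20 hrs".

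Other protocol text bears on continuation. The Table of Assessments (7.2) says NAC continues as per TOXBASE, and section 5 refers to standardised guidelines. Section 16.6 describes further NAC in the setting of deranged liver function.

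**The concern.** There are two separate points.

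The first is the treatment rule. The protocol is consistent with itself here, so this is not a conflict between protocol and SAP. It is a unit that makes one of four decision criteria unreachable. A patient whose 10-hour sample shows residual paracetamol, with ALT and INR below their triggers, would not qualify for more NAC under the text of 7.1.8. Under the synopsis, such a patient stays in hospital for a further 10 hours with one sample at 8 hours. A clinician who continued NAC for a level of, say, 30 mg/L would be departing from the literal rule, while section 16.2 restricts unapproved deviations. The rule also influences two quantities the SAP reports: additional NAC infusions (4.3) and duration of hospital stay (4.8).

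The second is the exploratory outcome. Protocol section 4 and SAP 4.5 define what is evidently the same outcome with thresholds that differ by a factor of 1,000. This is the only direct contradiction between the two documents on this point.

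**Working it through.** **Inputs from the documents**
- Threshold in the protocol: 20 mg/mL (synopsis, 3.1, 4, 7.1.8).
- Threshold in the SAP: 20 mg/L (4.5).
- Ingested dose that starts NAC in late or staggered presenters: "ingested greater than 12 g (or 150 mg/kg) paracetamol" (Protocol 3.1). This is a floor, not a ceiling.
- Second NAC bag: 200 mg/kg in 1000 mL (Protocol 7.1.7).
- Decision sample at 10 h, end of regimen at 12 h, next sample at 20 h.

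**Assumptions, not from the documents:** body weight 70 kg; distribution volume V from 0.05 L/kg (all drug confined to plasma) to 1.0 L/kg; complete immediate absorption and no elimination. Ignoring elimination favours reaching the threshold.

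**1. Conversion.** 20 mg/mL × 1,000 = 20,000 mg/L. Ratio to the SAP: 20,000 / 20 = 1,000.

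**2. Scale from document figures alone.** For the treatment-trigger dose to give 20 mg/mL, 12,000 mg / 20 mg/mL = 600 mL; per kilogram, 150 mg/kg / 20 mg/mL = 7.5 mL/kg. The whole dose would have to remain in that volume.

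**3. Bounding check over V.** Amount needed in the body = 20,000 mg/L × V × 70 kg. Concentration from 12 g = 12,000 mg / (V × 70 kg).

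| V (L/kg) | Amount needed for 20 mg/mL | Concentration from 12 g |
|---|---|---|
| 0.05 | 70 g | 3,429 mg/L |
| 0.2 | 280 g | 857 mg/L |
| 0.6 | 840 g | 286 mg/L |
| 1.0 | 1,400 g | 171 mg/L |

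Per kilogram, the amount needed runs from 20,000 × 0.05 = 1,000 mg/kg to 20,000 × 1.0 = 20,000 mg/kg. That is 1,000 / 150 = 6.7 to 20,000 / 150 = 133 times the 150 mg/kg trigger. The smallest figure, 70 g, requires every milligram to be in plasma, with none eliminated, in a sample drawn 10 hours after NAC began.

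**4. A second scale.** At 70 kg the second NAC bag holds 200 × 70 = 14,000 mg in 1000 mL, or 14 mg/mL before any addition from the drug volume. The written criterion asks for a higher concentration of paracetamol in blood than the antidote has in its own bag.

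**5. Entry line.** Patients presenting within 8 hours enter with a "timed blood paracetamol concentration above the 100-line on the UK APAP overdose treatment nomogram". If that line is in mg/L (an assumption: it is the SAP's recording unit, and the figure is not shown), the continuation threshold as printed is 20,000 / 100 = 200 times the nominal entry line. At 20 mg/L it would be 20 / 100 = one fifth of it.

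**6. With the SAP's unit.** At 70 kg and V = 0.6 L/kg, 20 mg/L corresponds to 20 × 0.6 × 70 = 840 mg, about 0.84 g still in the body. Patients can meet that criterion.

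**7. Timing.** If NAC stops at 12 h, the gap to the next scheduled sample is 20 − 12 = 8 h.

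**The case against.** The strongest reply is that this is a typing error with no practical consequence. TOXBASE is named in 6.5 as the national standard for the decision to treat and in 7.2 for continuation. Section 9.5 says clinical toxicologists manage the study. The ALT and INR criteria still work, patients stay in hospital after NAC stops, and paracetamol is measured again at 20 hours, when the schedule again allows for NAC. If the laboratory reports in mg/L, staff would probably compare that number with 20 and act correctly. The SAP already uses mg/L, and the outcome concerned is exploratory.

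Most of this stands, and it is why actual harm is unlikely. It does not remove the error. The TOXBASE threshold is not reproduced in the protocol, so safe conduct depends on staff setting aside an explicit number in a treatment rule.

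A second reply is that a lost micro sign in text extraction would produce exactly this discrepancy, since 20 µg/mL equals 20 mg/L. This is possible but unlikely: the synopsis shows the sign correctly in its µmol/kg doses, and the threshold reads mg/mL in all four places. A look at the source document settles it.

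A third reply is that the missing time point in section 4 is no fault, because Protocol 12.1 leaves technical detail to the SAP. That is fair. Adding the time points is tidy but optional.

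**Conclusion.** The threshold is wrong as written and should be corrected. In the protocol it is 1,000 times the SAP's value, and the fourth continuation criterion cannot be met in practice. The factor of 1,000 and the 600 mL comparison rest on document figures alone. The wider impossibility argument uses assumed body weight and distribution volume, and its conclusion holds across the whole range shown.

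The consequence is limited. The other criteria and the references to outside guidance make harm unlikely, and the planned analysis of the threshold outcome does not change because the SAP uses mg/L. The reason to act is that the error sits in an operative rule for stopping or continuing an antidote. That mg/L was intended is an inference from the SAP; the documents do not state the TOXBASE value or the laboratory's reporting unit.

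**What to change.** Confirm the value against the TOXBASE guidance the protocol follows and against the laboratory's reporting unit, and check the source document for a lost symbol. Then change mg/mL to mg/L in four places in the protocol: the synopsis (end of treatment), section 3.1, the exploratory outcomes in section 4, and section 7.1.8. Send the site a short notice of the corrected continuation rule. Optionally, add the 10- and 20-hour time points to the section 4 outcome so that it reads the same as SAP 4.5. The SAP threshold needs no change.

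The cost is a wording amendment and one site notice. There is no effect on sample size, data collection or the planned analysis.

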7.1.9 Adverse events

Adverse events/ adverse reactions will be assessed at baseline, 2hr, 2.5hr 10hr, 20hr and 22hr and as part of follow up (section 7.1.10). A full physical exam will be carried out if AEs/SAEs are identified that require a more thorough exam to be performed and this will be recorded on the CRF.

Episodes and incidence of vomiting and retching will be recorded objectively by nursing staff on the AE log and reported as an SAE if classified as serious.

Adverse events will be recorded and reported as detailed in Section 11.

7.1.10 Follow-up

There will be no follow-up visit, but patients will be followed up using their electronic records. The following data is collected 7, 30 and 90 days after randomisation: Representation to hospital (any reason), representation with liver injury, repeat overdose, death and transfer to liver transplantation unit. Any AEs or SAEs identified will be recorded and reported.

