An independent monitoring board will review safety data after each dosing cohort of PP100-01 has been completed and before the next dosing cohort can be initiated. The SDMC will assess safety, unexpected toxicities and unexpected increased severity of toxicities in the experimental arms. They will also propose changes to the protocol and/or stop the study if indicated. All further patient enrolment will be paused pending advise from the SDMC if one of the following stopping rules have been met: 1. Patient death, admission to a Critical Care Unit or admission to a Liver Transplantation Unit due to any reason, or 2. One SUSAR that definitely or probably relates to either PP100-01 or NAC or both.

Statistical Methods:

A CONSORT diagram depicting the flow of participants through the study will be reported. Descriptive statistics will be used to report baseline characteristics by treatment group (PP100-01 groups A, B, C, or NAC alone) and overall: continuous variables will be summarised by the mean, standard deviation, median minimum and maximum; categorical variables will be summarised using the number and percentage in each category. We will keep missing data to an absolute minimum, but where there is missing data those records will be removed from the analysis; if missing data rates are substantial the effect of this will be investigated using sensitivity analyses. Binary outcomes (including the primary outcome) will be reported by treatment group and overall using the proportion and exact 95% confidence interval. Continuous, outcomes will be reported by treatment group and overall using the mean and 95% confidence interval. The full details will be provided in a separate Statistical Analysis Plan.

Study schedule:

Visit windows	Screen ing	0 (NAC treatment)	Baseline (Pre-PP100-01)	After 2 hrs	After 2.5 hrs	After 10 hrs	After 12 hrs	After 20 hrs	Discharge after 22 hrs	7 day follow up	30 day follow up	90 day follow up
Informed Consent	Х											
Eligibility Criteria	Х											
Enroled into trial	Х											
Treatment Allocation/randomisation	Х											
Bloods												
APAP conc level	Х					Х		Х				
INR /Prothrombin	Х			Х		Х		Х				
ALT (IU/L)	Х			Х		Х		х				
ALP (IU/L)	Х			Х		Х		х				
Bilirubin	Х			Х		Х		Х				
Creatinine	Х			Х		Х		Х				
Hb	Х					х		х				
Urea	Х					Х		Х				
Sodium	Х					х		х				
Potassium	Х					Х		х				
MCV	Х					Х		Х				
WBC	Х					х		Х				
Inflammation Biomarkers				Х		Х		х				
PP100-01 levels				Х		Х		Х				

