6 STUDY POPULATION

6.1 Number of Participants

We aim to recruit a total of 24 patients presenting with POD and requiring treatment with NAC to the study. We approximate this can be completed in a 6-12 months recruitment period.

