10.3 Detecting AEs and SAEs

All AEs and SAEs must be recorded from the time a participant consents to join the study until hospital discharge.

The Investigator should ask about the occurrence of AEs/SAEs during the infusion and until hospital discharge. Open-ended and non-leading verbal questioning of the participant should be used to enquire about AE/SAE occurrence. If there is any doubt as to whether a clinical observation is an AE, the event should be recorded.

Patient electronic records will be reviewed at 7 days, 30 and 90 days after discharge for AEs and SAEs.

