10.10 Independent Safety Data Monitoring Committee (SDMC)

An independent safety data monitoring committee (SDMC) will be appointed to review accumulating adverse event data and patient safety. The SDMC will evaluate the safety in relation to PP100-01 dosing step increase. The committee will give recommendations on the continuation or termination of the study by detection of any safety signals as early as possible in accordance with the SDMC Charter.

Proposed composition of SDMC will be: Chairperson, Hepatologist, Statistician, Independent Clinical Pharmacologist/Toxicologist.

During the period of recruitment into the study, interim analyses of in-hospital mortality/morbidity and of any other information that is available on major outcome events (including serious adverse events believed to be due to treatment) will be supplied, in strict confidence, to the Chairperson of the SDMC, along with any other analyses that the committee may request.

All further patient enrolment will be paused pending advise from the SDMC if one of the following stopping rules have been met: 1. Patient death, admission to a Critical Care Unit or admission to a Liver Transplantation Unit due to any reason, or 2. One SUSAR that definitely or probably relates to either PP100-01 or NAC or both.

All SMDC data review will be documented and all meetings will have written minutes, which will be filed in the Trial Master File (TMF) upon completion of the study.

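### The pause rule has no time limit, but no minimum follow-up or record search is required before a dose step, so a higher dose can open with a post-discharge trigger unseen

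*Protocol*

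**What the plan says.** **Pause rule.** Protocol Section 10.10, repeated in the synopsis: "All further patient enrolment will be paused pending advise from the SDMC if one of the following stopping rules have been met". The first rule is "Patient death, admission to a Critical Care Unit or admission to a Liver Transplantation Unit due to any reason". No time limit is attached.

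**Detection after discharge.** Section 10.3 records AEs and SAEs from consent to discharge. Section 7.1.10 then has no visit, only electronic records: "The following data is collected 7, 30 and 90 days after randomisation". The items are "Representation to hospital (any reason), representation with liver injury, repeat overdose, death and transfer to liver transplantation unit", together with any AEs or SAEs found. Critical care admission is not named there or in SAP Section 4.8. The 24-hour SAE clock in Section 10.5 starts when the investigator becomes aware.

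**Anchor.** Section 7.1.10 and SAP Section 4.8 count from randomisation. Section 10.3 counts from discharge: "Patient electronic records will be reviewed at 7 days, 30 and 90 days after discharge for AEs and SAEs".

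**Dose step.** The synopsis has the SDMC review safety data "after each dosing cohort of PP100-01 has been completed and before the next dosing cohort can be initiated". Section 6.6.1 requires allocation at one dose to be finished before the next starts. Neither states a minimum follow-up. Section 10.10 supplies the SDMC with "interim analyses of in-hospital mortality/morbidity", any other available information on major outcome events, and any further analyses that it requests.

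**Accrual.** For 24 patients: "We approximate this can be completed in a 6-12 months recruitment period" (Section 6.1).

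**The concern.** The rule and the means of detecting its triggers cover different periods. The rule reaches any death or unit admission at any time. Continuous recording ends at discharge, which the synopsis puts about 22 hours after NAC starts (12 + 10) for patients needing no further NAC. From then on, the protocol requires a look on three fixed days only. Fast reporting after awareness does not help if nobody has yet looked.

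The dose-step review is where this matters most. Completion is undefined, so the SDMC could meet before the last patients have had even the day-7 check, and without a fresh search for earlier patients who are between checks. The next patients would then receive a higher dose. Section 13.1 calls the risks of this co-treatment unknown, and Section 12.3 notes that PP100-01 has not been given to overdose patients on NAC. A patient who starts NAC at the 24-hour limit and leaves 22 hours later is about 46 hours from ingestion, so scheduled observation ends early in the clinical course.

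**Working it through.** **Inputs.** Three cohorts of 6 + 2 (Section 6.6.1); 24 patients in 6 to 12 months (Section 6.1); checks at days 7, 30 and 90 (Section 7.1.10). A month is taken as 30.4375 days. Accrual is assumed uniform, with no SDMC pauses.

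**Plan's own figure.** 3 × (6 + 2) = 24, which reproduces. It is a count with no power calculation behind it.

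**Accrual rate.**
- 6 months: 182.6 days / 24 = one patient per 7.6 days; a cohort of 8 takes 60.9 days.
- 12 months: 365.25 days / 24 = one patient per 15.2 days; a cohort of 8 takes 121.8 days.

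**Enrolments between an event and its detection** = longest gap between checks / days per patient.

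| Event falls just after | Found at | Gap (days) | 12 months | 9 months | 6 months |
|---|---|---|---|---|---|
| Day 1 | Day 7 | 6 | 0.4 | 0.5 | 0.8 |
| Day 7 | Day 30 | 23 | 1.5 | 2.0 | 3.0 |
| Day 30 | Day 90 | 60 | 3.9 | 5.3 | 7.9 |

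These are maxima. An event at a random point in a gap waits half as long on average (3, 11.5 and 30 days).

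**Chance that a whole cohort enrols in the 60-day gap.** With Poisson accrual (an assumption), P(8 or more) is 0.53 at 6 months, 0.16 at 9 and 0.05 at 12. In the 23-day gap it is at most 0.012.

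**Sensitivity.** If 56 days of SDMC pauses fall inside the same recruitment period (an assumption), accrual while open is faster. The 23-day gap then covers 1.8 to 4.4 patients and the 60-day gap nominally 4.7 to 11.4. The upper figure is not reachable if the pauses are split equally between the two steps: a cohort then fills in 42.2 days, so a 60-day gap runs into a pause.

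**Checks outstanding when patient 8 is enrolled.**
- Day 7: patient 7 entered 7.6 to 15.2 days earlier and is past day 7. One patient is outstanding, or two if accrual is bunched.
- Day 30: 30 / 15.2 = 2.0 to 30 / 7.6 = 3.9 patients are outstanding.

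**Cost of waiting for day 7.** 2 dose steps × 7 days = at most 14 days. The searches cover 8 patients, then 16.

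**The case against.** The strongest reply has five parts.

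- **SDMC data.** A reader might infer that the committee sees only in-hospital events. Section 10.10 does not support that: it adds any other available information and whatever the committee requests. The Charter may also set a minimum follow-up. This stands. But making available information available does not oblige anyone to look, and the protocol is where the pause rule sits.
- **A whole cohort late.** A reader might infer this from the 60-day gap. It needs an event just after day 30 at the fastest accrual. Early liver events would be found by day 7, within 0.4 to 0.8 enrolments. This stands. A delay of one patient is nevertheless enough to cross a dose step if it falls at the end of a cohort.
- **Who leaves at 22 hours.** Only patients needing no further NAC. Those meeting the continuation criteria in Section 7.1.8 remain on treatment in hospital (Section 5), and AEs open at discharge are followed up (Sections 10.1 and 10.7). This stands, but it does not catch a new event in a patient discharged well.
- **Critical care admission.** After discharge it would fall under representation for any reason and meet the hospitalisation criterion for an SAE. It is therefore not uncaptured; naming it is a small clarification.
- **Likelihood.** Triggers should be rare. Section 2.2.1 cites a retrospective series of 1270 patients, mostly on the 20.25-hour regimen, with no deaths and one transplant. The roughly 25% in Section 2.1 is hepatotoxicity, which is not a trigger, and the 8 to 72 hours in Section 3.3 translates mouse treatment times and does not date serious outcomes. Neither should be used to predict trigger rates.

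A reader might also infer that completion cannot mean 90-day follow-up. Two such waits (180 days) would nearly fill a 6-month period, but they fit within 12 months, and a 7- or 30-day minimum is not excluded. The term is undefined, no more than that.

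**Conclusion.** The concern holds for the dose-step decision. Followed as written, the protocol allows a higher dose to open while an event that should have paused enrolment sits unseen in the records. The exposed group is small for recent discharges: typically the last one or two patients of a cohort lack the day-7 check. For earlier patients between checks, an unseen event can be overtaken by about 1.5 to 3 enrolments (to day 30) or 4 to 8 (to day 90), with 8 only the worst case at 6-month accrual.

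This rests on uniform accrual at the stated rate, on post-discharge events not reaching the team by another route before a check, and on the Charter not already requiring follow-up data or a search. The documents do not support saying that nobody would have looked: at the stated accrual the day-7 check would normally have fallen due for most of the cohort. The two anchors for the checks are a plain inconsistency, worth about a day for a patient who leaves at 22 hours and more for one who stays longer.

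**What to change.** In Section 10.10 and the synopsis:

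1. State that a cohort counts as completed for SDMC review only when the day-7 record check is done for all its patients.
2. Require that, before each dose-step review, the electronic records of every patient enrolled so far are searched to the data cut for death, critical care admission, liver-unit transfer and readmission, with the results in the SDMC package.

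In Section 7.1.10 and SAP Section 4.8, name critical care admission as an item. Reconcile the anchor between those sections and Section 10.3. Align the Charter if it is silent or differs.

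Doses and the pause rule are untouched. The cost is wording, two record searches (8, then 16 patients), and a wait of up to about 7 days at each of two dose steps, at most 14 days in a 6- to 12-month recruitment period.

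The limit should be stated openly. A cohort takes about 61 to 122 days to fill, so searches at dose steps leave the detection lag within a cohort largely as it is, and the third cohort has no later step to trigger a search.
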